
Objectives
	
1. To establish and implement an infrastructure for longitudinal remote follow-up of phase 3 trial cohorts:
 
 
a. Transition from site-based to a centralized site and coordination center to manage all participant activity in virtual extensions of SURE-PD3, with projected enrollment of <math>\geq 70\%</math> of final trial cohorts, and core data collection in accordance with Parkinson’s Disease Biomarkers Program (PDBP) schedule of activities.
 
b. Conduct an annual research visit (tele-visit) program and establish the feasibility and cross-sectional reliability of tele-visit versus in-person visit assessments in a subset of STEADY-PD III and SURE-PD3 participants.
 
c. Deploy a smartphone application, based on the mPower study, for remote data collection in a clinical trial cohort as preliminarily characterized in the Smart4SURE sub-study of SURE-PD3.
 
d. Establish a mechanism for linking STEADY-PD III and SURE-PD3 study data with data collected through smartphone-based assessments, tele-visits, and Fox Insight (FI), a separate longitudinal patient-reported outcomes (PROs) online research study.
 
 
2. To compare patient-driven (smartphone, web-based surveys) vs clinician-driven (tele-visit) outcomes by:
 
 
a. Correlating the smartphone and tele-visit platforms’ component and composite features, and their changes over years.
 
b. Comparing the smartphone and tele-visit platforms’ abilities to: i) measure PD progression and predict clinical events and changes in PROs; ii) distinguish rapid vs slow progressors based on baseline Movement Disorders Society-Unified Parkinson’s Disease Rating Scale (MDS-UPDRS) scores, dopamine transporter (DAT) deficit (in SURE-PD3) or serum urate levels (in STEADY-PD III); iii) demonstrate persistence of any effects of isradipine or inosine in their respective trials.
 
c. Comparing completion status and performance on FI and tele-visit PROs.
 
 
3. To explore novel smartphone-based real-life mobility biomarkers of PD disability and its progression that are normally inaccessible with traditional office measures. We will investigate the ability of passively collected smartphone data on ambulation and location to enable assessments of physical activity and

	socialization that correlate with motor and non-motor functions.

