
Statistical Analysis (by Specific Aim)
	
SA 1: We will use results from the REACT-PD study to establish a calibration of tele-visit (TV) assessments to predict in-clinic MDS-UPDRS scores (Aim 1b). Lin's concordance correlation coefficient, <math>r_c</math>, will be used to summarize accuracy of the calibrated TV estimates vs. scores collected from in-person SURE-PD3 visits conducted close in time, accepting TV estimates as sufficiently accurate if <math>r_c > 0.8</math>. If we observe insufficient concordance, we will recalibrate using all available data from both REACT-PD and the current study.
 
SA 2: The study sample will be randomly split 2:1 into calibration and validation subsets. The calibration sample will be used to derive smartphone (SP) measures that best match the TV assessed composite scores of motor function (MDS-UPDRS part 3), non-motor function (MoCA total score), subjective function (including clinical global impression [CGI] scores, patient global impression scores, modified Schwab and England ADL scores, and MDS-UPDRS parts 1b and 2 scores), and estimates of MDS-UPDRS part 1-3 total scores (Aim 2a). The accuracy of calibrated SP measures will be tested in the reserved validation sample using Lin's concordance correlation coefficient, <math>r_c</math>. If we observe insufficient concordance, we will recalibrate using all available data from both the calibration and validation samples.
 
TV assessments and calibrated SP measures of disease progression will be compared generally and between specific subsets of participants expected to progress at different rates (Aim 2b). Each measure will be standardized to 30% of the observed mean change over 2 years based on a random-slopes linear mixed model of the full sample such that a one-unit change of all standardized, calibrated measures would reflect an equivalent magnitude of change relative to natural rates of progression. Estimated measure-specific variance components will be used to estimate the standard error for a treatment group comparison from a two-arm trial assuming an assessment schedule appropriate for a given measure, e.g., annual for TV measures and quarterly for SP measures. The ratio of squared standard errors will be used to estimate the relative sample size required using one or another measure for designs with equivalent power. The same approach will be used to identify measures that are sensitive to biological subgroups (e.g., among participants stratified by their rate of MDS-UPDRS progression over the first 2 years of in-clinic follow-up in the parent trials) or treatment-based subgroups (e.g., participants randomized to isradipine or serum urate elevation). TV assessments and SP measures will also be compared with respect to their accuracy in predicting future clinical events and changes in

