
Power Calculations
	
SA 1b. With a sample size of ~10 SURE-PD3 participants expected to complete at least one TV close in time to their in-person clinic visit, the study will have 80% power to conclude that the REACT-PD calibrated tele-visit estimates are sufficiently accurate (<math>r_c > 0.8</math> at <math>\alpha = 0.05</math>) if the true concordance is at least 0.89.
 
SA 2a. With a 2:1 split of ~340 AT-HOME PD participants, yielding ~115 participants contributing to validation tests, the study will have 80% power to declare a given SP measure sufficiently accurate (<math>r_c > 0.80</math> at <math>\alpha = 0.05</math>) if the true concordance is at least 0.87.
 
SA 2b. With approximately 80% of participants participating in the SP portion of the study, yielding ~340 participants contributing to the smartphone vs tele-visit comparison, the study would have an 80% probability of selecting the true preferred measure from a pair of TV or SP if the preferred measure had lower standard error by an effect size of at least 0.065.
 
SA 3. With a 2:1 split of ~240 participants, yielding ~80 in the validation sample and at least 25% experiencing at least an 8-point progression in MDS-UPDRS parts 1-3 total score, the study would have 80% power to declare a novel measure derived from passive SP monitoring to have a ROC AUC significantly greater than 0.80 if the true AUC were at least 0.95.

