Data Management	
Data collected during tele-visits will be entered and maintained in REDCap (a secure web-based survey and data management system). Each participant’s baseline demographic information, concomitant medications, and health history as well as clinical data including PD-PROP from the corresponding SUPER-PD visit, will be transferred from the SUPER-PD REDCap project to the AHPD sub-study REDCap project. All data will ultimately be transferred to Synapse (an open source collaborative platform) for analysis. For any sub-study participants who are participating in the mPower 2.0 component of SUPER-PD, their smartphone data from the corresponding SUPER-PD visit and associated remote 2-week burst will be linked with AT-HOME PD data within Synapse.
 
From Synapse, the cleaned, processed, and event date- and time-transformed dataset will be transferred to the PDBP’s Data Management Resource for further distribution to PDBP investigators and will be made available to the wider research community through their qualified researchers program.

Statistical Analysis	Paired MDS-UPDRS and MoCA scores from in-person and TV assessments of SUPER-PD participants will be pooled with data from SURE-PD3. The accuracy of predicted in-clinic scores based

	
on TV assessments using calibrations from REACT-PD will be summarized by Lin's concordance correlation coefficient, <math>r_c</math>, equivalent to an intra-class correlation (ICC). The REACT-PD calibrations will be judged sufficiently accurate if <math>r_c > 0.8</math>. If we observe insufficient concordance, we will re-calibrate using all available data from REACT-PD, SURE-PD3, and SUPER-PD.

Sample Size	
With a combined sample size of ~60 SURE-PD3 and SUPER-PD participants expected to complete at least one TV close in time to their in-person clinic visit, the study will have 80% power to conclude that the REACT-PD calibrated tele-visit estimates are sufficiently accurate (<math>r_c > 0.8</math> at alpha = 0.05) if the true concordance is at least 0.89.

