## 2. STUDY OBJECTIVE

### 2.1 Specific Aims:

**1. To establish and implement an infrastructure for longitudinal remote follow-up of phase 3 trial cohorts:**

- a. Transition from site-based to a centralized site and coordination center to manage all participant activity in virtual extensions of STEADY-PD III and SURE-PD3, with projected enrollment of  $\geq 70\%$  of final trial cohorts, and core data collection in accordance with Parkinson's Disease Biomarkers Program (PDBP) schedule of activities.
- b. Conduct an annual research visit (tele-visit) program and establish the feasibility and cross-sectional reliability of tele-visit versus in-person visit assessments in a subset of SURE-PD3 and SUPER-PD participants.
- c. Deploy a smartphone application, based on the mPower study, for remote data collection in a clinical trial cohort as preliminarily characterized in the Smart4SURE sub-study of SURE-PD3.
- d. Establish a mechanism for linking STEADY-PD III and SURE-PD3 study data with study data collected through smartphone-based assessments, tele-visits, and Fox Insight (FI), a separate longitudinal patient-reported outcomes (PROs) online research study.

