## 13.2 Statistical Analysis Plan

**Aim 1:** To evaluate concordance between in-clinic and tele-visit MDS-UPDRS assessments (Aim 1b), we will use results from the REACT-PD study to calibrate tele-visit assessments to in-clinic MDS-UPDRS scores, matching means and standard deviations cross-sectionally. We will use Lin's concordance correlation coefficient,  $r_c$ , to summarize accuracy of the calibrated tele-visit estimates vs. scores collected from in-person SURE-PD3 and SUPER-PD visits conducted close in time, accepting tele-visit estimates as sufficiently accurate if  $r_c > 0.8$ . If we observe insufficient concordance, we will investigate contributions of bias, scale difference, and imprecision and re-calibrate using all available data from both REACT-PD and the current study.

**Aim 2:** We will assess the calibration and correlation between tele-visit (TV) and SP metrics both cross-sectionally and longitudinally (Aim 2a). We will generate SP-derived metrics that best match composite scores of motor function (MDS-UPDRS part 3), non-motor function (MoCA total score), subjective function (including global impression (CGI) scores, Schwab and England ADL scores, MDS-UPDRS parts 1b and 2 scores, and estimates of MDS-UPDRS part 1-3 total scores. We will randomly split our sample 2:1 into calibration and validation subsets. For each measure, we will use the calibration sample to develop a transformation of SP data that best matches the TV measurement machine learning models using a variety of machine learning techniques with a final selection based on overall accuracy by 10-fold cross-validation. We will test the accuracy of calibrated SP measures in the reserved validation sample using Lin's concordance correlation coefficient,  $r_c$ . If we observe insufficient concordance, we will investigate contributions of bias, scale difference, and imprecision and re-calibrate using all available data from both the calibration and validation samples.

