#### 13.4 Sample Size Determination

SA 1b. With a sample size of ~10 SURE-PD3 and ~50 SUPER-PD participants expected to complete at least one TV close in time to their in-person clinic visit, the study will have 80% power to conclude that the REACT-PD calibrated tele-visit estimates are sufficiently accurate ( $r_c > 0.8$  at  $\alpha = 0.05$ ) if the true concordance is at least 0.89.

SA 2a. With a 2:1 split of ~340 AT-HOME PD participants, yielding ~115 participants contributing to validation tests, the study will have 80% power to declare a given SP measure sufficiently accurate ( $r_c > 0.80$  at  $\alpha = 0.05$ ) if the true concordance is at least 0.87.

SA 2b. With approximately 80% of participants participating in the SP portion of the study, yielding ~340 participants contributing to the smartphone vs tele-visit comparison, the study would have an 80% probability of selecting the true preferred measure from a pair of TV or SP if the preferred measure had lower standard error by an effect size of at least 0.065.

SA 3. With a 2:1 split of ~240 participants, yielding ~80 in the validation sample and at least 25% experiencing at least an 8-point progression in MDS-UPDS parts 1-3 total score, the study would have 80% power to

declare a novel measure derived from passive SP monitoring to have a ROC AUC significantly greater than 0.80 if the true AUC were at least 0.95.

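### Main Synopsis SA 1b claims 80% power from about 10 pairs; that sample gives roughly 21–24%, and the same figures are attached elsewhere to about 60 pairs

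*Combined protocol and SAP*

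**What the plan says.** Three places give a power statement for SA 1b, the check of calibrated tele-visit scores against in-person scores. All three share the acceptance threshold (r_c > 0.8), alpha (0.05), power (80%) and true concordance (0.89). They differ in sample size.

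- Protocol Synopsis, SA 1b entry under Power Calculations: "With a sample size of ~10 SURE-PD3 participants expected to complete at least one TV close in time to their in-person clinic visit".
- Section 13.4, SA 1b entry: "With a sample size of ~10 SURE-PD3 and ~50 SUPER-PD participants expected to complete at least one TV".
- SUPER-PD sub-study synopsis, Sample Size: "With a combined sample size of ~60 SURE-PD3 and SUPER-PD participants expected to complete at least one TV".

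The cohorts named for this aim also differ between Synopsis and body. The Synopsis analysis text for SA 1 compares tele-visit estimates with "scores collected from in-person SURE-PD3 visits conducted close in time", whereas Section 13.2 (Aim 1) uses "scores collected from in-person SURE-PD3 and SUPER-PD visits conducted close in time". Objective 1b in the Synopsis places the reliability work "in a subset of STEADY-PD III and SURE-PD3 participants", whereas Section 2.1 places it "in a subset of SURE-PD3 and SUPER-PD participants".

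The companion calculation for SA 2a reads "With a 2:1 split of ~340 AT-HOME PD participants, yielding ~115 participants contributing to validation tests" and claims 80% power against the same 0.80 threshold at a true concordance of 0.87. None of these statements says whether alpha is one- or two-sided.

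**The concern.** With threshold, alpha and true concordance fixed, power is determined by the number of pairs. The same inputs cannot give 80% power at both 10 and 60 pairs, so at least one statement is wrong, and the main Synopsis is where many readers will look.

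This test decides whether tele-visit scores are accepted as accurate substitutes for in-clinic scores. Section 1.2 reports a REACT-PD intra-class correlation of only 0.53 for MDS-UPDRS Part III, before the calibration planned here, so the size of the validation sample matters. Someone relying on the Synopsis could conclude that about 10 pairs suffice and that the 50-participant sub-study is unnecessary. Section 13 also says a separate SAP will override the protocol in a conflict, so its authors need one unambiguous figure to carry forward.

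**Working it through.** **Inputs.** Threshold r0 = 0.80, alpha = 0.05, and true concordance 0.89 for SA 1b or 0.87 for SA 2a (Synopsis Power Calculations and Section 13.4). Pairs: about 10 (main Synopsis), about 60 (Section 13.4 and the sub-study synopsis), about 115 (SA 2a).

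**Formula.** On the Fisher z scale,

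power = Φ[(atanh r1 − atanh 0.80) × √(n − k) − z_crit],

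with z_crit = 1.645 one-sided or 1.960 two-sided. The constant k depends on the form of the coefficient: 3 for Pearson, 2 for Lin, 1.5 for an intra-class correlation (the sub-study synopsis treats r_c as equivalent to one). All three are shown.

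atanh 0.80 = 1.0986, atanh 0.89 = 1.4219 and atanh 0.87 = 1.3331, so the differences are 0.3233 (SA 1b) and 0.2345 (SA 2a).

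**The plan's figures, then the disputed one:**

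| n | true r_c | one-sided power (k = 3 / 2 / 1.5) | two-sided power (k = 3 / 2 / 1.5) | plan |
|---|---|---|---|---|
| 60 | 0.89 | 78.7 / 79.3 / 79.6% | 68.5 / 69.2 / 69.6% | 80% |
| 115 | 0.87 | 79.9 / 80.2 / 80.3% | 69.9 / 70.3 / 70.5% | 80% |
| 10 | 0.89 | 21.5 / 23.3 / 24.1% | 13.5 / 14.8 / 15.4% | 80% |

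Worked example, n = 10 and k = 3: 0.3233 × √7 = 0.855; 0.855 − 1.645 = −0.790; Φ(−0.790) = 0.215. For n = 60: 0.3233 × √57 = 2.441; 2.441 − 1.645 = 0.796; Φ(0.796) = 0.787.

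The 60-pair and 115-pair figures both reproduce one-sided and neither does two-sided. The 10-pair figure reproduces on neither basis. The overstatement one-sided is 80/24.1 = 3.3 to 80/21.5 = 3.7.

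**Simulation check.** Because the normal approximation is rough at n = 10, Lin's coefficient was simulated under bivariate normality with equal means and SDs. With a simulated 5% critical value (200,000 replicates), power was 24.1% at n = 10 and 79.6% at n = 60 one-sided, and 14.9% and 69.9% two-sided. Using Lin's estimated variance on the z scale (100,000 replicates), one-sided power was 20.5% at n = 10 and 78.2% at n = 60. Applying the k = 2 critical value directly to the simulated coefficients gave 17.4% and 77.7%. No version brings n = 10 near 80%.

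**What each sample can detect at 80% power:** r_c = tanh[atanh 0.80 + (z_crit + 0.8416)/√(n − k)].

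- n = 10: 0.960–0.967 one-sided, 0.968–0.974 two-sided.
- n = 60: 0.890–0.891 one-sided, 0.899–0.900 two-sided.
- n = 115: 0.870 one-sided, 0.877 two-sided.

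Conversely, 80% power at 0.89 needs 61–63 pairs one-sided or 77–79 two-sided. The 0.89 figure therefore belongs to about 60 pairs and a one-sided test.

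**The case against.** The strongest defence of the Synopsis figure is that the acceptance rule, read literally, asks only for an observed r_c above 0.8. With 10 pairs that happens 79% of the time at a true value of 0.89, which looks like the claimed 80%. But the same rule accepts 44% of the time when the true value is exactly 0.80, which contradicts the alpha of 0.05 in the same sentence. It would also give 99% at n = 60, so it cannot explain the other two statements. This reading fails.

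A second objection concerns weight. The error sits in one sentence; the sub-study synopsis that follows it, Section 13.2 and Section 13.4 all carry the pooled sample. No participant, analysis or decision rule changes. This stands, and it limits the point to a correction of the Synopsis.

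Third, the sidedness can be inferred: the claim tested is directional, and the two workable calculations agree with a one-sided alpha. That is fair, and a short clarification is enough.

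Fourth, the cohort mismatch in Objective 1b may be innocent. REACT-PD drew its 40 participants from STEADY-PD III (Section 1.2), and the Synopsis may mean those calibration data. It does not say so.

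Finally, the main Synopsis may be meant to cover SURE-PD3 alone, since the sub-study has its own synopsis. The documents do not settle this, so the choice of correction belongs to the authors.

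**Conclusion.** The concern holds. With about 10 pairs and a true concordance of 0.89, power is about 21–24% one-sided or 13–15% two-sided by formula, against the stated 80%. In the main Synopsis, the sample size and the detectable concordance cannot both be right. The same pair of figures is sound for about 60 pooled participants if alpha is one-sided; two-sided power there is 68–70%.

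The result assumes one pair per participant and a test of r_c against 0.80 that holds alpha at 0.05. The simulations also assume bivariate normality with equal means and SDs. The conclusion does not depend on the variance form, the sidedness, or the choice of formula over simulation. It should be fixed, but it is a misstatement in the Synopsis and not a design defect.

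**What to change.** 1. Reconcile the SA 1b sentence in the main Synopsis with Section 13.4. Either adopt the Section 13.4 sample (about 10 SURE-PD3 plus about 50 SUPER-PD) or, if the Synopsis is meant to cover SURE-PD3 only, keep about 10 and give the detectable concordance as about 0.96–0.97 (one-sided). If the pooled figure is used, note that about 60 pairs exist only for MDS-UPDRS Part 3 and MoCA, the outcomes assessed at the SUPER-PD tele-visit.
2. State the sidedness of alpha wherever these calculations appear: main Synopsis, sub-study synopsis and Section 13.4. One-sided matches the existing figures. If two-sided was intended, restate the detectable concordance as about 0.90 for 60 pairs and about 0.88 for 115.
3. Align the Synopsis SA 1 analysis text with Section 13.2, and Objective 1b with Section 2.1. If STEADY-PD III in Objective 1b refers to the REACT-PD calibration data, say so.

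The cost is wording only: no added participants and no change of analysis. Keeping about 10 participants makes the published detectable concordance less favourable.

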**AHPD – SUPER-PD TELE-VISIT VALIDATION SUB-STUDY SYNOPSIS**

Study Center	University of Rochester
Objectives	To establish the cross-sectional reliability of tele-visit versus in-person research visit assessments of participants with PD
Study Population	Individuals with PD enrolled in the University of Rochester’s on-going S ensor U se to Monitor P rogression and E valuate Symptoms R emotely in P arkinson’s D isease (SUPER-PD) study
Study Design	Individuals with PD from SUPER-PD will complete a single tele-visit within ±2 weeks of their SUPER-PD baseline or month 12 in-person study visit.
Number of Participants	Approximately 50
Main Inclusion Criteria	
 
1. Enrollment in SUPER-PD
 
2. Diagnosis of idiopathic PD (as determined by UK Parkinson’s Disease Brain Bank Criteria in SUPER-PD)
 
3. Have consented to future contact by the University of Rochester
 
4. Internet-enabled device that will support participation in tele-visits
 
5. Willing and able to provide informed consent
 

Main Exclusion Criteria	
 
1. Inability to carry out study activities
 

Study Rationale	Tele-visits offer the promise of streamlining study conduct and reducing the burden on study participants. The objective of this sub-study is to establish the cross-sectional reliability of tele-visit assessments.
Study Outcome Measures	
 
• MDS-UPDRS part 3
 
• Montreal Cognitive Assessment
 

Data Management	
Data collected during tele-visits will be entered and maintained in REDCap (a secure web-based survey and data management system). Each participant’s baseline demographic information, concomitant medications, and health history as well as clinical data including PD-PROP from the corresponding SUPER-PD visit, will be transferred from the SUPER-PD REDCap project to the AHPD sub-study REDCap project. All data will ultimately be transferred to Synapse (an open source collaborative platform) for analysis. For any sub-study participants who are participating in the mPower 2.0 component of SUPER-PD, their smartphone data from the corresponding SUPER-PD visit and associated remote 2-week burst will be linked with AT-HOME PD data within Synapse.
 
From Synapse, the cleaned, processed, and event date- and time-transformed dataset will be transferred to the PDBP’s Data Management Resource for further distribution to PDBP investigators and will be made available to the wider research community through their qualified researchers program.

Statistical Analysis	Paired MDS-UPDRS and MoCA scores from in-person and TV assessments of SUPER-PD participants will be pooled with data from SURE-PD3. The accuracy of predicted in-clinic scores based

	
on TV assessments using calibrations from REACT-PD will be summarized by Lin's concordance correlation coefficient, <math>r_c</math>, equivalent to an intra-class correlation (ICC). The REACT-PD calibrations will be judged sufficiently accurate if <math>r_c > 0.8</math>. If we observe insufficient concordance, we will re-calibrate using all available data from REACT-PD, SURE-PD3, and SUPER-PD.

Sample Size	
With a combined sample size of ~60 SURE-PD3 and SUPER-PD participants expected to complete at least one TV close in time to their in-person clinic visit, the study will have 80% power to conclude that the REACT-PD calibrated tele-visit estimates are sufficiently accurate (<math>r_c > 0.8</math> at alpha = 0.05) if the true concordance is at least 0.89.

